3.8.2.4. Patient Reported Cellulite Impact Scale (PR-CIS)

Subjects will answer the PR-CIS at Screening (within 14 days after Day 71/EOS of double-blind study), Day 180, Retreatment Phase [Screening B and Day 71 (End of Treatment/Early Termination)], and Observation Assessments Visits [Day 360, 540, 720, and 1080/EOS].

The PR-CIS is a 6-item static questionnaire assessing the visual and emotional impact of cellulite (happy, bothered, self-conscious, embarrassed, looking older or looking overweight or out of shape); each item is answered by the subject on an 11-level numerical rating scale from 0 (not at all) to 10 (extremely) while viewing digital images of their buttocks. This assessment is of both the left and right buttock together rather than each individual buttock separately.

A PR-CIS total score and an abbreviated PR-CIS score (excluding question 5) will be derived from 6 individual questions mentioned in Table 9 below:

Table 9: Patient Reported Cellulite Impact Scale (PR-CIS) Questions

Question No.	Question
1	Thinking about the areas selected for treatment, how happy are you with the appearance of your cellulite?
2	Thinking about the areas selected for treatment, how bothered are you by the appearance of your cellulite?
3	Thinking about the areas selected for treatment, how self-conscious are you about the appearance of your cellulite?
4	Thinking about the areas selected for treatment, how embarrassed are you about the appearance of your cellulite?
5	Thinking about the areas selected for treatment, how much older do you look because of your cellulite?
6	Thinking about the areas selected for treatment, how overweight or out of shape do you look because of your cellulite?

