4.4.3. Patient Reported Cellulite Impact Scale Total Score

A PR-CIS total score and an abbreviated PR-CIS score (excluding question 5) will be derived from 6 individual questions (refer to section 3.8.2.4) for a region, ie, two buttocks during evaluation.

The PR-CIS total score will be derived by adding the ratings of the 6 items on the scale. Item #1 on the PR-CIS asking – “how happy the subject is about their appearance of cellulite” will be reversed by subtracting the subject’s reported assessment from 10 (ie, for purposes of the composite, scoring for the “happy” question is reversed (reflected) to make it directionally consistent with the other questions). In this manner, a higher number on 6 of the PR-CIS questions will reflect a more negative impact.

The PR-CIS total score will range from 0 to 60 with higher numbers reflecting more negative impact from the cellulite. If scores on two or less of the 6 items are missing, then the PR-CIS total score will be calibrated to 6 and computed as:

- Total PR-CIS Score = (Sum of the Scores ÷ Number of questions answered) x 6

If scores on three or more of the 6 items are missing, then the PR-CIS total score will be set to missing.

Similarly, the PR-CIS abbreviated total score will be derived by adding the sum of the five items (Items #1-4 and Item #6) on the scale (note that for the abbreviated total score Item #1 score should be replaced by the value generated by subtracting the item score from 10). The PR-CIS abbreviated total score will range from 0 to 50 with higher numbers reflecting more negative impact from the cellulite. If scores on two or less of the 5 items are missing, the PR-CIS abbreviated total score will be computed as:

- Abbreviated total PR-CIS Score = (Sum of the Scores ÷ Number of questions answered) x 5

If scores on three or more of the five items are missing, then the PR-CIS abbreviated total score will be set to missing.

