4.4.3.2. Responders based on Baseline PR-CIS Item or Total or Abbreviated Total Scores

A PR-CIS (item or total or abbreviated total) responder with respect to Day 1 of double-blind study is defined as a subject with a reduction in the PR-CIS score (item or total or abbreviated total) of at least 2 from Day 1 of double blind study at an evaluation time point.

A PR-CIS (item or total or abbreviated total) responder with respect to Day 71/EOS of double-blind study is defined as a subject with a reduction in the PR-CIS score (item or total) of at least 2 from Day 71/EOS of double blind study at an evaluation time point.

A PR-CIS (item or total or abbreviated total) responder with respect to Day 1 of retreatment period of this study is defined as a subject with a reduction in the PR-CIS score (item or total) of at least 2 from Day 1 of retreatment period of this study at an evaluation time point.

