7.6.7. Responder Analysis based on Baseline PR-CIS Scores

The PR-CIS responders (Each item, Total, and Abbreviated) will be analyzed separately at Day 180 using Day-180 Observational Population, for the data before retreatment using TRR Population Before Retreatment, and data after retreatment using OLR Population.

At Day 180 Evaluation

The proportion of PR-CIS responders based on item scores, total, and abbreviated scores (refer to section 4.4.3) of the subjects in 180 – Day Observational Population will be summarized using frequency counts and percentages by treatment arm (ie, CCH 1.68 mg, Placebo, and Overall) at overall treatment area (ie, two buttocks).

Before Retreatment

The proportion of PR-CIS responders based on item scores, total, and abbreviated scores (refer to section 4.4.3) of the subjects who did not receive retreatment and the data until the point prior to retreatment for the subjects who are retreated will be summarized using frequency counts and percentages for subjects in TRR Population Before Retreatment by subject category (ie, Category I and II, and Overall) at overall treatment area (ie, two buttocks) and assessment visits: Day 180, Month 12, 18, 24, and 36.

After Retreatment

The proportion of PR-CIS responders based on item scores, total and abbreviated scores (ie, based on scores as compared to baseline - refer to section 4.4.3) at Day 71 of the retreatment session and other observational visits of the subjects who are retreated in the open label study will be summarized using frequency counts and percentages for subjects in OLR Population by subject category (ie, Category I and II, and Overall) at overall treatment area (ie, two buttocks).

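### The PR-CIS responder rule uses one 2-point cut-off for the 0–10 items, the 0–60 total and the 0–50 abbreviated total, so sum-score responder rates are not comparable with item rates and can be heavily inflated by random variation

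*SAP*

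**What the plan says.** SAP section 3.8.2.4 has each of the six PR-CIS questions answered on an "11-level numerical rating scale from 0 (not at all) to 10 (extremely"). Section 4.4.3 builds the totals as sums, not means: "The PR-CIS total score will be derived by adding the ratings of the 6 items on the scale". It gives the resulting ranges as "The PR-CIS total score will range from 0 to 60 with higher numbers reflecting more negative impact from the cellulite" and "The PR-CIS abbreviated total score will range from 0 to 50 with higher numbers reflecting more negative impact from the cellulite". The abbreviated score drops question 5. Item 1 (happiness) is reversed when the totals are formed.

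Section 4.4.3.2 then sets the responder rule for three reference points:

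- Double-blind Day 1: "a reduction in the PR-CIS score (item or total or abbreviated total) of at least 2 from Day 1 of double blind study".
- Double-blind Day 71: "a reduction in the PR-CIS score (item or total) of at least 2 from Day 71/EOS of double blind study".
- Retreatment Day 1: "a reduction in the PR-CIS score (item or total) of at least 2 from Day 1 of retreatment period of this study".

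The second and third definitions open by naming all three kinds of score, although the later parenthesis omits the abbreviated total.

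Section 7.6.7 uses the rule: "The PR-CIS responders (Each item, Total, and Abbreviated) will be analyzed separately at Day 180 using Day-180 Observational Population", and likewise before and after retreatment. Section 7.6.8 adds a responder analysis against Day 71 of the open-label period. The SAP gives no reason for the value 2 and does not rescale it for the sums.

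**The concern.** A cut-off of 2 has one meaning on a 0–10 item and quite another on a sum of five or six such items. The total-score rule asks for far less change per item than the item rule, yet both results are reported as PR-CIS responder proportions in the same analyses. A reader who sees a higher rate on the total than on the items could take it as broader benefit, when the difference may come only from the cut-off.

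The second risk is the background rate. If a small total-score movement counts as response, many subjects whose condition has not changed will qualify through ordinary variation in their answers. Placebo subjects leave the study after unblinding, so only the Day 180 tables show a placebo rate. The tables before retreatment (listed for Day 180 through Month 36) and after retreatment are split by subject category, with no comparator to show how many responders the rule produces by chance.

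**Working it through.** **No stated figure to reproduce.** The SAP gives no SD, reliability, expected change or expected responder rate for PR-CIS. Its ranges do reproduce: 6 × 10 = 60 and 5 × 10 = 50.

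**Step 1: the cut-off relative to each scale (no assumptions).**

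| Score | Range | 2 as share of range | Mean change per item |
|---|---|---|---|
| Item | 0–10 | 2/10 = 20% | 2.00 |
| Total | 0–60 | 2/60 = 3.3% | 2/6 = 0.33 |
| Abbreviated total | 0–50 | 2/50 = 4.0% | 2/5 = 0.40 |

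Relative to range, the rule is 20/3.3 = 6 times more lenient on the total and 20/4 = 5 times more lenient on the abbreviated total. A subject who drops one point on two items and is unchanged on the rest has a total change of −2. She is a responder on the total and on no item.

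**Step 2: interaction with prorating (no assumptions).** Section 4.4.3 rescales the total to six items when one or two are missing. Take five items at 5 and one at 8 (after reversal of Item 1): total 25 + 8 = 33. If the item scored 8 is left blank at the next visit and every other answer is identical, the total is 25/5 × 6 = 30. That is a reduction of 3, so she is a responder without having changed any answer.

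**Step 3: background rate with no true change (assumptions needed).** Let s be the SD of change on one item and ρ the correlation between item changes. Neither is in the SAP. I took s = 1 to 2 and ρ = 0 to 0.6, with s = 1.5 and ρ = 0.3 as the middle case. I used a normal approximation with continuity correction for whole-number scores:

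- SD of total change = s√(6 + 30ρ)
- SD of abbreviated change = s√(5 + 20ρ)
- P(responder at cut-off t) = Φ(−(t − 0.5)/SD)

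Middle case:

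- Item: Φ(−1.5/1.5) = 15.9%
- Total: SD = 1.5 × √15 = 5.81; Φ(−1.5/5.81) = 39.8%
- Abbreviated: SD = 1.5 × √11 = 4.97; Φ(−1.5/4.97) = 38.2%

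Both sum scores are then repeated at cut-offs scaled from the item rule, 2 × 6 = 12 and 2 × 5 = 10:

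| Score | Cut-off 2: middle (range) | Scaled cut-off: middle (range) |
|---|---|---|
| Item | 16% (7–23%) | unchanged |
| Total | 40% (27–44%) | at 12: 2.4% (0–12%) |
| Abbreviated | 38% (25–43%) | at 10: 2.8% (0–12%) |

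Widening the assumptions to s = 1 to 3 and ρ = 0 to 0.8 gives 7–31% for an item, 27–46% for the total and 25–46% for the abbreviated total at cut-off 2.

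**The case against.** The strongest reply is that a high background rate among unchanged subjects does not show what the observed rates are made of. A reader might infer that the total-score rates mostly count random drift. The documents do not support that, because it depends on the true change and its SD, and the SAP gives neither. For an assumed SD of total change of 5 to 12, the rate at cut-off 2 is 38–45% with no true change, 55–62% with a mean change of −3, and 92–100% with a mean change of −18. Chance could account for much of the rate in the first two settings. In the last, nearly everyone qualifies because nearly everyone improved.

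A reader might also infer that the rule cannot separate CCH from placebo at Day 180. That does not follow either. Both arms are tabulated and random variation affects both. With SD 5.81 and mean changes of −6 and 0, cut-off 2 gives Φ(4.5/5.81) = 78% against 40%, a gap of 38 points. Cut-off 12 gives Φ(−5.5/5.81) = 17% against 2%, a gap of 15. With −12 against −6 the order reverses: 18 points at cut-off 2 and 36 at cut-off 12. A higher cut-off is not always the better discriminator.

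It is also fair that 12 and 10 are the item rule scaled up, not a validated threshold; that PR-CIS is in neither the primary nor the secondary objective; and that sections 7.6.5 and 7.6.6 summarize scores and changes directly, without this rule.

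These points limit the conclusion. They do not explain why one absolute value should serve scales of length 10, 50 and 60, and nothing in the SAP does.

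**Conclusion.** The mismatch of scale is certain from the SAP's own definitions: the sum-score rule is five to six times more lenient than the item rule relative to range, so the rates are not comparable. The inflation is conditional. If there is no true change, item-change SD is 1–2 and inter-item correlation is 0–0.6, about 27–44% of subjects would be responders on the total and 25–43% on the abbreviated total, against 7–23% on an item. The rates can therefore be heavily inflated by random variation; by how much in this trial cannot be said from the documents. The problem matters most in the tables before and after retreatment, which have no placebo column. As these are descriptive, non-primary summaries, the change should be made, but no main conclusion of the study depends on it.

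**What to change.** In section 4.4.3.2:

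- Keep a reduction of at least 2 for single items, and apply it to Item 1 after reversal. Section 4.4.3 states the reversal only for the totals, and section 4.4.3.1 treats an increase on Item 1 as improvement. As written, a 2-point worsening on raw Item 1 would count as response.
- Set the cut-off at 12 for the total (2 × 6) and 10 for the abbreviated total (2 × 5), each 20% of its range. This fits the SAP's own prorating, which treats the total as six times the item mean. If the sponsor has a documented meaningful-change threshold for either sum score, state and use that instead.
- Apply the cut-offs to all three reference points, naming the abbreviated total throughout, and add a definition for the open-label Day 71 reference, which section 7.6.8 uses and section 4.4.3.2 does not define.

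The cost is SAP wording and a few programming constants, with no new data. Reported sum-score responder rates will be lower. Section 6.4 planned a Day 180 analysis for the licence application. Any outputs from it that used the 2-point cut-off for the totals (the SAP does not show whether they did) must be re-run or shown alongside the new ones.

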4.4.3.1. Change from Baseline of PR-CIS Item or Total or Abbreviated Total Scores

The change from Day 1 of the double-blind study for PR-CIS is defined as PR-CIS score (item or total or abbreviated total) at respective visit minus PR-CIS score at Day 1 of the double-blind study.

The change from Day 71/EOS of the double-blind study for PR-CIS is defined as PR-CIS score (item or total or abbreviated total) at respective visit minus PR-CIS score at Day 71/EOS of the double-blind study.

The change from Day 1 of retreatment period for PR-CIS score (item or total or abbreviated total) will be the visit score minus the Day 1 of retreatment period score.

For Item #1, a more positive change in score indicates a greater improvement of impact of the cellulite on subject's happiness while for other items a more negative change in score indicates a greater reduction of impact of the cellulite on subject's life.

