Baseline for Reduction of response and Improvement in Cellulite Severity (CR-PCSS and PR-PCSS)	
Improvement in Cellulite Severity: The assessment performed at Day 1 during the retreatment phase will be used as baseline to evaluate improvement in cellulite severity at Day 71 in this study.
 
Reduction of Response Prior to Retreatment: The assessment performed at Day 71/EOS visit in the double-blind phase will be used as baseline to evaluate reduction of response for any visits prior to/on first dose date of retreatment in this study.
 
Reduction of Response After Retreatment: The assessment performed at Day 71/End of treatment Session in the retreatment phase will be used as baseline to evaluate reduction of response during the observation phase after retreatment.

Baseline for CR-PCSS, PR-PCSS and PR-CIS Score	
At 180 Day Evaluation: The Screening assessment done within 14 days of Day 71/EOS of double-blind period will be used as baseline for 180 Day Evaluation period.
 
Before Retreatment: The Screening assessment done within 14 days of Day 71/EOS of double-blind period will be used as baseline for open-label period for subjects in TRR population who are not retreated, and until the point prior to retreatment for the subjects who are retreated.
 
After Retreatment: The assessments at Screening B/unscheduled assessment or Day 1 of the retreatment phase prior to/on the first dose date of retreatment in this study will be used as baseline.

Baseline for S-GAIS and Subject Satisfaction with Cellulite Treatment	The pretreatment Day 1 digital images from the double-blind study (EN3835-302/303) will be used as baseline.
Change from Baseline	Change from baseline will be derived as, post-baseline visit/time point value – the baseline value.
Time to reduction of response prior to retreatment (duration in days)	Date of visit where reduction is detected first – Date of Day 71/EOS of double-blinded studies 302/303
Time to reduction of response after retreatment (duration in days)	Date of visit where reduction is detected first – Date of Day 71/End of Treatment Session of open-label retreatment phase
Time to Complete Loss of Response prior to retreatment (duration in days)	Date of visit where complete loss of response reduction is detected first – Date of Day 71 of double-blinded studies 302/303 OR Date of Day 71/End of Treatment Session of open-label retreatment phase

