7.6.8. Responder Analysis based on Day 71 Open-label Period PR-CIS Scores

The proportion of PR-CIS responders based on item scores, total and abbreviated scores (ie, based on scores as compared to Day 71 of open-label period - refer to section 4.4.3) at observational visits after retreatment will be summarized using frequency counts and percentages for subjects in OLR Population by subject category (ie, Category I and II, and Overall) at overall treatment area (ie, two buttocks).

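### The Day 71-referenced PR-CIS responder rule cannot separate maintained from lost benefit, and SAP 7.6.7 does not commit to the double-blind Day 1 reference that avoids this

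*SAP*

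**What the plan says.** SAP 4.4.3.2 gives three PR-CIS responder definitions, each a fall of at least 2 points from a reference score:

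- **Double-blind Day 1** (before any treatment): "reduction in the PR-CIS score (item or total or abbreviated total) of at least 2 from Day 1 of double blind study".
- **Double-blind Day 71/EOS** (after the course): "reduction in the PR-CIS score (item or total) of at least 2 from Day 71/EOS of double blind study at an evaluation time point".
- **Retreatment Day 1** (before retreatment): a fall "of at least 2 from Day 1 of retreatment period of this study at an evaluation time point".

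On direction, 4.4.3 states: "The PR-CIS total score will range from 0 to 60 with higher numbers reflecting more negative impact from the cellulite". Item #1 (happiness) is reversed when the total and abbreviated total are built. When it is analysed as an item, 4.4.3.1 keeps its raw direction: "For Item #1, a more positive change in score indicates a greater improvement of impact of the cellulite".

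Table 17 in section 6.2 sets the PR-CIS baseline. For Day 180: "The Screening assessment done within 14 days of Day 71/EOS of double-blind period will be used as baseline for 180 Day Evaluation period". For the period before retreatment, the same Day 71/EOS assessment "will be used as baseline for open-label period for subjects in TRR population who are not retreated", and it also serves retreated subjects up to retreatment. After retreatment the baseline is a pre-retreatment score.

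Section 7.6.7 is titled as a responder analysis on baseline PR-CIS scores. It covers Day 180, Months 12-36 before retreatment, and visits after retreatment. For the first two it refers only to 4.4.3 and does not say which reference applies. Section 7.6.8 adds responders after retreatment, "based on scores as compared to Day 71 of open-label period - refer to section 4.4.3".

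**The concern.** No study drug is given between Day 71 of a course and the observation visits that follow it. The question at those visits is whether benefit lasts; the secondary objective is time to reduction of response. A rule that asks for another 2-point fall from the post-treatment score answers a different question, namely who went on improving. A subject who keeps all of the benefit and one who loses all of it are both non-responders, so the percentage says nothing about durability.

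For PR-PCSS and CR-PCSS the plan handles this correctly: Table 13 and Table 17 take Day 71 as the reference and count worsening. The PR-CIS has no equivalent. At stake is whether the long-term PR-CIS responder tables can be read as evidence on lasting patient-reported benefit.

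**Working it through.** The SAP gives no expected PR-CIS responder rate, SD or sample size, so there is no figure to reproduce. The check applies the rule as written: responder if (reference score − visit score) ≥ 2.

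**1. Which reference 7.6.7 uses.** Its title says baseline, and Table 17 puts that baseline at Day 71/EOS for Day 180 and before retreatment. Section 7.6.5, on change scores, shows the drafting habit: baseline is Day 71/EOS, and double-blind Day 1 is named separately when it is also wanted. Section 7.6.7 does not name Day 1. Day 71 is therefore the natural reading, though not the only possible one.

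**2. Which definition 7.6.8 uses.** It compares with Day 71 of the open-label period and points to 4.4.3. None of the three definitions in 4.4.3.2 has that reference. Carrying over the reduction rule gives the same behaviour as the Day 71/EOS definition.

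**3. Classification on the total score.** Assumed values: 42 at double-blind Day 1, 24 at Day 71.

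| Later score | Day 71 − score | Day 71 rule | Day 1 − score | Day 1 rule |
|---|---|---|---|---|
| 22 (further gain) | 2 | responder | 20 | responder |
| 24 (maintained) | 0 | non-responder | 18 | responder |
| 26 (2 points lost) | −2 | non-responder | 16 | responder |
| 33 (half lost) | −9 | non-responder | 9 | responder |
| 42 (fully lost) | −18 | non-responder | 0 | non-responder |

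The Day 71 rule puts everything from maintenance to full loss in one class. The Day 1 rule separates maintenance from full loss but still calls a half-lost benefit a response. The same logic holds for the abbreviated total and items 2-6. On any of items 2-6, a subject at 0 or 1 on Day 71 cannot meet the Day 71 rule at all.

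**4. Item #1, unreversed.** Assumed values: 2 at Day 1, 7 at Day 71.

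- Day 71 rule: a fall back to 2 gives 7 − 2 = 5, responder. Staying at 7 gives 0 and rising to 9 gives −2, both non-responder. Loss is counted as response.
- Day 1 rule: staying at 7 gives 2 − 7 = −5, non-responder. The improvement is not recognised.

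**5. What the Day 71 rate shows when benefit is maintained on average.** Assume change from Day 71 is normal with mean 0. P(responder) = P(change ≤ −2) = Φ(−2/SD):

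- SD 2: Φ(−1.0) ≈ 16%
- SD 5: Φ(−0.4) ≈ 34%
- SD 10: Φ(−0.2) ≈ 42%

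These SDs are assumptions. In this setting the rate reflects visit-to-visit variation only.

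**6. Size of the threshold.** 2/10 = 20% of an item's range, 2/60 = 3.3% of the total's range and 2/50 = 4% of the abbreviated total's range. By symmetry, a 2-point worsening rule on the total would label the same 16%, 34% or 42% of subjects as worse when nothing has changed on average.

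**The case against.** The strongest reply is that Day 71 is one of three references. Under the double-blind Day 1 definition a maintained benefit is a response and a full return is not. Section 7.6.7 does not name Day 71/EOS before retreatment, its title echoes that of 4.4.3.2, which holds all three definitions, and the table shells that might settle the reference are in SAP Module 2, which is not shown. After retreatment 7.6.7 uses a pre-retreatment baseline, so 7.6.8 is an additional table there. Durability is carried mainly by PR-PCSS and CR-PCSS, S-GAIS is rated against pretreatment images, and satisfaction and SSRS responders use absolute ratings. The PR-CIS responder tables are descriptive, with no test. Further improvement after Day 71 is a coherent, if narrower, question.

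Most of this stands, and it limits the point. A reader might infer that PR-CIS responders are always judged against Day 71, or that loss of benefit never appears. The documents do not support either. The Day 1 and retreatment Day 1 definitions exist. Sections 7.6.5 and 7.6.6 summarise change from Day 71 before and after retreatment, so average worsening would be seen. A reader might also infer a responder rate of exactly 0% under both perfect maintenance and complete loss. That needs zero visit-to-visit variation, and it fails for Item #1.

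What the reply does not remove is that 7.6.7, read with Table 17, leads to the Day 71 rule; that 7.6.8 uses a Day 71 reference explicitly; and that a mean change does not say how many subjects kept or lost benefit.

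**Conclusion.** The point holds for the Day 71-referenced analyses: the second definition in 4.4.3.2, 7.6.7 at Day 180 and before retreatment as read with Table 17, and 7.6.8. On the total, the abbreviated total and items 2-6 these cannot tell maintained from lost benefit. On Item #1 the literal rule runs backwards, and this affects every reference. Section 7.6.7 leaves the usable Day 1 definition uncommitted, and 7.6.8 cites a definition that is not there.

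The classification results follow from the rule itself. The example scores, the normal model and the SDs of 2 to 10 are assumptions. Because the analyses are descriptive, no error rate or primary conclusion is affected. The consequence is that the long-term PR-CIS responder percentages could be misread as evidence on durability. The change should be made before the tables are produced.

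**What to change.** 1. In 7.6.7, name double-blind Day 1 as the responder reference at Day 180 and at Months 12-36 before retreatment. Keep the pre-retreatment baseline after retreatment.
2. For both Day 71 references (double-blind, and retreatment in 7.6.8), replace the responder count with the number and percentage worsened, unchanged and improved relative to Day 71, in line with the direction used in Table 13. Define the retreatment Day 71 comparison in 4.4.3.2. This keeps the information on further improvement and adds partial loss, which the Day 1 rule misses.
3. Reverse Item #1 before any item-level rule is applied, and say so in 4.4.3.2.
4. State the threshold separately for items, total and abbreviated total, with a reason for each. Two points on the 0-60 total would largely capture visit-to-visit variation, in either direction.

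The cost is SAP wording and table shells. All the scores are already collected, and no visit, assessment or test changes.
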